3.8.3 Secondary analyses

- **Demographic and clinical profile**

Demographics and baseline clinical characteristics of patients (as outlined in Table 3) will be summarized using descriptive statistics.

- **Progression free survival**

Progression free survival is defined in Table 2. This will be assessed for first-line treatments and described graphically by Kaplan-Meier (KM) survival curves. Median PFS, 25th and 75th percentiles, and corresponding 95% CI will be reported. Cox regression analysis may be performed to adjust for predefined (baseline) covariates and HR and 95% CIs reported.

- **Overall survival**

Overall survival is defined in Table 2. This will be described graphically by KM survival curves and median OS, 25th and 75th percentiles, and correspondent 95% CI reported. Cox regression analysis may be performed to adjust for predefined (baseline) covariates; HRs and 95% CIs will be reported.

- **Treatment response**

The category of objective response following treatment (CR, PR, and PD) will be summarized by first-line SACT treatments (monotherapy, doublet therapy, triplet therapy) and by treatment regimens using frequency tables with their associated 95% CIs. Additionally, ORR is defined in Table 2. Logistic regression may be used to adjust for predefined (baseline) covariates; odds ratios with 95% CIs will be reported.

- **Treatment duration (time to treatment cessation)**

Time to treatment cessation (defined in Table 2) will be assessed for first-line SACT treatments. This will be described graphically by KM survival curves. Cox regression may be used to adjust for predefined (baseline) covariates; HRs and 95% CIs will be reported.

- **BRAF Mutation testing**

Time from metastatic diagnosis to BRAF mutation testing will be assessed in addition to the time from testing to first-line treatment, and all testing procedures will be summarized using descriptive statistics.

- **Safety analyses**

The number and percentage of patients who have at least one of the relevant AE during first-line treatment will be summarized. Clopper-Pearson (Exact) 95% CIs for the proportion will be constructed around the point estimate of the incidence. Tables with counts and frequencies of relevant AEs will be provided and summarized by MedDRA SOC and PT.

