2.2 SECONDARY OBJECTIVES

The secondary objectives are:

1. To describe the baseline demographic and clinical profiles of BRAF^{V600E} mutant mCRC patients receiving first-line treatment, overall and by treatment regimen
2. To describe PFS in BRAF^{V600E} mutant mCRC patients receiving first-line treatment, overall and by treatment regimen
3. To describe OS in BRAF^{V600E} mutant mCRC patients receiving first-line treatment, overall and by treatment regimen
4. To describe treatment response in BRAF^{V600E} mutant mCRC patients receiving first-line treatment, overall and by treatment regimen
5. To describe treatment duration (i.e., time from treatment initiation to treatment cessation) in BRAF^{V600E} mutant mCRC patients receiving first-line treatment, overall and by treatment regimen
6. To describe BRAF mutation testing procedure and timing in regards with the first-line treatment in BRAF^{V600E} mutant mCRC patients
7. To describe the frequency of relevant AEs in BRAFV600E mutant mCRC patients receiving first-line treatment, overall and by treatment regimen. Relevant AEs are defined as AEs leading to first-line treatment switch, dose adaptation or discontinuation, or leading to death.

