3.3 STUDY OUTCOMES

3.3.1 Primary endpoint

The primary endpoints are first-line SACT treatment patterns in BRAF^{V600E} mutant mCRC patients, described by:

- Agent or combination of agents received
- Duration of treatment
- Maintenance therapy (if any)

The first-line SACT regimen(s) will be described from the time of treatment initiation (for mCRC) until the time of first documented disease progression, treatment discontinuation or switch, whichever is earlier.

LOT definition will be connected to treatment progression. The LOT will be defined using a data-driven approach. In the SAP an algorithm for LOT definition will be specified, which will consider the specific treatment(s) received (stop and start dates), progression (as recorded in the patient medical record, including date), documented reasons for discontinuation of treatments and gap(s) between subsequent treatment regimens.

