3.3.2 Secondary endpoints

1. Description of the demographic and clinical profile of patients at the time of treatment initiation (for mCRC)
2. PFS, defined as the length of time between initiation of first-line treatment for mCRC and the first documented disease progression (if disease progression is not well documented in a patient's medical record, then the start of the subsequent LOT may be considered as proxy for disease progression) or death (whichever is earlier)
3. OS, defined as the length of time between first-line treatment initiation (for mCRC) and death (due to any cause)
4. ORR, defined as complete response (CR) or partial response (PR), described at the end of first-line treatment for mCRC
5. Time to treatment cessation, defined as the length of time between initiation of firstline treatment for mCRC and documented disease progression (or start of subsequent LOT, if disease progression is not well documented in the patient medical record), treatment discontinuation or switch to another treatment (defined as change from 1 treatment regimen to another treatment regimen, e.g. change from FOLFOX-based regimen to FOLFIRI or irinotecan-based regimen)
6. Time to BRAF mutation testing since mCRC diagnosis and since first-line treatment for mCRC, and description of testing procedures
7. Frequency of relevant AEs during first-line treatment for mCRC. Relevant AEs are defined as AEs leading to first-line treatment switch, dose adaptation or discontinuation, or leading to death.

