3.3.4 Exposure definition and measurement

This is a NIS of real-world treatment practices in the adult BRAF^{V600E} mutant mCRC patient population. This protocol does not recommend the use of any specific treatments, and no study medication will be provided as part of participation in the study.

The exposure of interest will be the first-line SACT (monotherapy, doublet therapy, or triplet therapy with or without a targeted therapy [either VEGF inhibitor or EGFR inhibitor]) for the treatment of BRAF^{V600E} mutant mCRC. Treatment patterns will be described by LOT.

Line of therapy will be defined as follows:

- First LOT: the start of first LOT will be defined as the first administration of SACT therapy after diagnosis of mCRC to the date of first documented disease progression
- Second and subsequent LOTs: mCRC treatment(s) received on or after the date of documented disease progression following previous LOT to the date of documented disease progression on or after the current LOT
- In the absence of information on disease progression, an algorithm will be specified in the SAP based on the specific treatment(s) received (stop and start dates), progression (as recorded in the patient medical record, including date), documented reasons for discontinuation of treatments and gap(s) between subsequent treatment regimens.

The exposure variables of interest are described in Table 1.

Table 1 Study Exposure

Exposure	Definition and Measurements
Systemic anti-cancer therapy (SACT) ¹ for mCRC	
 Details on SACT (by LOT) 
 LOT² (e.g., first, second, third, etc.) Type of treatment³ (i.e., monotherapy, doublet therapy, triplet therapy) Agents used 
 Chemotherapy regimens (e.g., FOLFOX, FOLFIRI, FOLFOXIRI) Targeted agents (e.g., bvacizumab, cetuximab, panitumumab) Duration of treatment: start date and stop date Date of documented progression Dates and reasons for treatment alteration (e.g., switch, discontinuation, dose escalation/reduction) Maintenance therapy (if any) of first line treatment: name of agent(s); start date and stop date Treatment response (as recorded in patient medical record by the treating physician) of first-line treatment of mCRC: type of response (CR, PR, PD); date recorded

¹ All SACT treatments received/prescribed for mCRC will be captured.

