Relevant Adverse events	
 Time to treatment cessation is defined as the length of time between initiation of first-line treatment and documented disease progression (or start of subsequent LOT, if disease progression is not well documented in patient medical record), treatment discontinuation or switch to another treatment (defined as change from 1 treatment regimen to another). Time to treatment cessation will be calculated from the date of initiation of LOT to the date of disease progression, treatment discontinuation or switch. Patients with no disease progression, treatment discontinuation or switch to another treatment will be censored at the earliest of: date of last medical record entry, last day of the observation period or date of death.
Cause of death (for deceased patients)	
 Information on relevant AEs during the study period will be collected based on information available in the patient medical records. Relevant AEs will be mapped into the (MedDRA) and grouped by SOC and PT. 
Relevant AEs are defined as AEs leading to first-line treatment switch, dose adaptation or discontinuation, or leading to death.

Reasons for treatment discontinuation or switch	
 The primary cause of death will be recorded as available in the medical record (cancer-related, non-cancer related, unknown/missing). Reasons for treatment alteration, defined as treatment interruptions, switches and discontinuation, will be collected at the end of each treatment, based on information available in the patient medical records.

¹ For patients in whom disease progression is not well documented, the start date of subsequent LOT will be considered instead of the date of disease progression. Detailed derivation of LOT will be provided in the SAP.

CR: complete response; ICD-10: International Classification of Diseases 10th Revision; mCRC: metastatic colorectal cancer; MedDRA: Medical Dictionary for Regulatory Activities; LOT: line of therapy; ORR: overall response rate; OS: overall survival; PD: progressive disease; PFS: progression free survival; PR: partial response; PT: preferred term; SOC: system organ class.

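### The crude percentage of patients with a relevant AE, reported by regimen, mixes AE hazard with time on first line; fixed-time cumulative incidence and patient-months would separate the two at little cost

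*Combined protocol and SAP*

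**What the plan says.** Secondary objective 7 (section 2.2) is "To describe the frequency of relevant AEs in BRAFV600E mutant mCRC patients receiving first-line treatment, overall and by treatment regimen". A relevant AE is defined by its consequence: "Relevant AEs are defined as AEs leading to first-line treatment switch, dose adaptation or discontinuation, or leading to death" (section 3.3.2).

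The safety paragraph of section 3.8.3 gives the method: "The number and percentage of patients who have at least one of the relevant AE during first-line treatment will be summarized", and "Clopper-Pearson (Exact) 95% CIs for the proportion will be constructed around the point estimate of the incidence". It adds counts and frequencies by MedDRA system organ class and preferred term. It states no person-time rate, time to first AE or cumulative incidence, and does not itself mention regimen; that comes from the objective.

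The first-line window is described in two ways. Section 3.3.4 runs it from "the first administration of SACT therapy after diagnosis of mCRC to the date of first documented disease progression". Section 3.3.1 describes first-line regimens "until the time of first documented disease progression, treatment discontinuation or switch, whichever is earlier". The AE window varies too. Table 2 has "Information on relevant AEs during the study period will be collected based on information available in the patient medical records", the synopsis refers to follow-up, section 3.8.3 to first-line treatment, and note 8 to Table 4 restricts AE collection to first line.

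Table 1 lists "Duration of treatment: start date and stop date", with dates and reasons for treatment alterations. Table 4 lists date of death. Section 3.8.1 calls the analysis descriptive and leaves full methods to a SAP to be written before database lock. That SAP is not in the text supplied.

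**The concern.** A patient who progresses at 2 months can contribute a first-line AE for only 2 months; one controlled for a year has a year in which to have one. The crude percentage counts both as complete observations. The length of the window is itself an outcome of the regimen, and PFS and time to cessation by regimen are separate secondary objectives precisely because they may differ. Those endpoints are handled by Kaplan-Meier with censoring; the AE summary alone ignores time.

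The reader at risk is the one who sets the regimens side by side. The study rationale says that the results are to put the single-arm ANCHOR trial into context and may support health technology assessment. ANCHOR also treats until progression or toxicity (among other reasons for stopping), so its crude AE percentages carry the same dependence on exposure time.

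**Working it through.** **The plan's own figure.** The only design figure is the precision of a regimen share: 1.96 × √(p(1−p)/300) gives ±2.47, ±3.39 and ±4.53 points for p = 5%, 10% and 20%, as in Table 5. These shares imply regimen groups of 300 × p = 15, 30 and 60 patients. The documents state no AE rate.

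**Inputs from the protocol (section 1).** Median PFS of 5.4 months (irinotecan-based) and 6.4 months (oxaliplatin-based), P = 0.99. PFS hazard ratio 0.57 (95% CI 0.27 to 1.23) for FOLFOXIRI plus bevacizumab against FOLFIRI plus bevacizumab, from 28 BRAF-mutant patients.

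**Assumptions.** Monthly hazard h of a first relevant AE, equal in both regimens, 0.03 to 0.10. First line ends for other reasons at a constant rate μ = ln 2 / median. The HR of 0.57 is applied to 5.4 months: 5.4/0.57 = 9.5 months. This gives μ = 0.1284, 0.1083 and 0.0732 for medians of 5.4, 6.4 and 9.5 months.

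**Crude percentage, risk continuing through the window:** h/(h+μ).

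| h per month | 5.4 mo | 6.4 mo | 9.5 mo | 6.4 − 5.4 | 9.5 − 5.4 |
|---|---|---|---|---|---|
| 0.03 | 18.9% | 21.7% | 29.1% | 2.8 | 10.1 |
| 0.06 | 31.9% | 35.7% | 45.1% | 3.8 | 13.2 |
| 0.10 | 43.8% | 48.0% | 57.7% | 4.2 | 14.0 |

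Toxicity per month is identical across each row.

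**Early risk only.** With h = 0.10 confined to the first 1.5 months (assumed), the percentage is h/(h+μ) × (1 − exp(−1.5(h+μ))): 12.7% for 5.4 months and 13.2% for 9.5 months, a gap of 0.5 point.

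**Higher early, lower later.** With 0.12 per month to 1.5 months and 0.04 afterwards (assumed), the percentage is 0.12/(0.12+μ) × (1 − exp(−1.5(0.12+μ))) + exp(−1.5(0.12+μ)) × 0.04/(0.04+μ): 31.4% and 42.1%, still about 11 points.

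**Reversal.** Crude percentages are equal when the ratio of AE hazards equals the ratio of μ: 5.4/6.4 = 0.84, or 0.57. Below that, the longer-control regimen shows the lower figure. At 0.05 against 0.10 per month it shows 40.6% (9.5 months) against 43.8% (5.4 months).

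**Fixed-time cumulative incidence, end of first line competing:** h/(h+μ) × (1 − exp(−(h+μ)t)). At h = 0.06, for 5.4 and 9.5 months:
- t = 3: 13.8% and 14.8%, gap about 1 point.
- t = 6: 21.6% and 24.8%, gap about 3 points.
- Whole window: 31.9% and 45.1%, gap about 13 points.

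**Rate per patient-month when risk is early.** In the 1.5-month case, mean time at risk is (1 − exp(−1.5(h+μ)))/(h+μ) + exp(−1.5(h+μ))/μ = 6.80 and 11.86 months. The rates are 0.127/6.80 = 1.87 and 0.132/11.86 = 1.11 per 100 patient-months. That is about 40% lower for the longer-control regimen although the hazards are identical.

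**The case against.** A reader might infer that regimens with longer disease control must show more AEs. The documents do not support that. It needs equal hazards, risk that persists through the window, and windows that really differ. The gap nearly disappears with early risk and can reverse. Relevant AEs include those that cause discontinuation or switch, which close the section 3.3.1 window, so a short window may itself reflect toxicity. The HR interval includes 1: at its upper limit of 1.23 the second median is 5.4/1.23 = 4.4 months, and h = 0.06 gives 27.5% against 31.9%, the other direction. The 5.4-month median comes from a different, retrospective study that reported no PFS difference, and the protocol says that FOLFOXIRI plus bevacizumab increases grade 3 or 4 AEs in mCRC, so equal toxicity is only an illustration for that pair. All of this stands.

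Sampling error is also large: an observed 40% has an exact 95% interval of 16 to 68% at n = 15, 23 to 59% at n = 30 and 28 to 54% at n = 60. This limits what any by-regimen AE figure can show, but does not remove the mixing.

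The proportion of starters with a relevant AE during first line is a legitimate descriptive quantity and matches the endpoint as worded. Treatment duration (section 3.8.2) and time to cessation by regimen are reported elsewhere, so a careful reader has part of the context, and the SAP may supply more. This argues for keeping the percentage and for modest priority. Separate duration tables still do not separate hazard from time at risk.

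Two further points limit the remedy. A patient-month rate should not lead, because it misleads when risk is front-loaded. AE onset date is not among the listed data items, so events may have to be timed by alteration or death date.

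**Conclusion.** The point holds as a cheap improvement to a descriptive secondary analysis. The crude percentage by regimen does not account for differing time at risk, so differences between regimens mix AE hazard with time on first line. With equal hazards and continuing risk, the longer window adds about 4 points (2.8 to 4.2) for 5.4 against 6.4 months and 10 to 14 points for 5.4 against 9.5 months. The AE hazards and the 9.5-month median are assumptions, and the HR behind the latter is imprecise. The documents establish neither that windows differ materially between regimens nor which way the crude comparison would err. Patients still on first line at 31 January 2020 are a minor part: starts closed on 31 December 2018, so follow-up is potentially at least 13 months. With uniform starts over 36 months and exponential windows, (exp(−13μ) − exp(−49μ))/(36μ) gives about 4% and 6% at medians of 5.4 and 6.4 months. No sample size or precision figure changes.

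**What to change.** In section 3.8.3, Safety analyses, and in the SAP:

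1. Keep the crude percentage with its Clopper-Pearson interval, and show patient-months at risk beside it for each regimen.
2. Add, by regimen, the cumulative incidence of first relevant AE at 3 and 6 months with 95% CIs. Treat end of first line without a relevant AE as the competing event, and censor patients still on first line at 31 January 2020. Base by-regimen AE statements on these figures.
3. Report the first-event rate per 100 patient-months, with an exact Poisson 95% CI, as supportive only, and state that it misleads when risk is front-loaded.
4. Where no AE onset date is recorded, time the event by the treatment alteration or death that makes it relevant, and say so in a footnote.
5. Reconcile the AE window across the synopsis, Table 2, note 8 to Table 4 and section 3.8.3, and state which end of first line applies, since sections 3.3.1 and 3.3.4 differ.

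The cost is some wording and one extra table from treatment, alteration and death dates already collected. The cumulative incidence keeps a small dependence on progression, about 1 point at 3 months and 3 points at 6 months in the 0.06 per month example.

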3.8.4 Exploratory analyses

- **Reason(s) for treatment alteration**

The reasons for treatment alteration (dose change, interruptions, switches, discontinuation), as recorded in patient medical records, will be described using descriptive statistics.

- **Treatment patterns for second (and subsequent) LOT**

Second- (and subsequent-) line treatment patterns, in the subset of patients who progress beyond first-line treatment, will be analyzed based on the methods described in primary analysis (Section 3.8.2).

3.8.5 Missing data

Due to the nature of the study, missing data (i.e., data that are not collected or documented in the patient's medical record or EMR) may be observed for some variables. In general, missing data will not be imputed (except for dates) and the data will be analyzed according to complete case approach. Partial dates will be imputed using the rules described in the SAP.

3.9 QUALITY CONTROL

A study monitoring plan, including for-cause monitoring, that is appropriate for the study design will be developed and implemented. Data quality control (QC) will be performed remotely and, where permissible according to local regulations, at the site level by qualified designated personnel under professional secrecy. The extent and nature of monitoring will be decided during the study planning based on design, complexity, number of subjects, number of sites, etc.

During a site initiation call, the monitor will provide training on the conduct of the study to the investigator, co-investigator(s), and all site staff involved in the study. In order to ensure the integrity of the data, eCRFs will be remotely monitored and, where permissible according to local regulations, sites will be randomly visited for quality control. Site quality control, if performed, will be performed by the contractor to examine compliance with the protocol and adherence to the data collection procedures, to assess the accuracy and completeness of submitted clinical data, and to verify that records and documents are being properly maintained for the duration of the study.

The monitor will close out each site after the last patient's final data collection is completed, all data have been entered and all outstanding monitoring issues have been resolved or addressed. All monitoring procedures and frequency of monitoring visits will be described in the study monitoring plan. Monitor contact details for each participating site will be maintained in the Investigator Site File.

In most cases, the source documents are contained in the patient's medical record and data collected on the eCRFs must match the data in the medical records. All original source documentation is expected to be stored at the site for the longest possible time required by locally applicable regulations.

Representatives of the Sponsor's quality assurance unit/monitoring team and competent regulatory authorities must be permitted to inspect all study-related documents and other materials at the site, including the Investigator Site File and the completed eCRFs. Patients' original medical records will only be examined if permitted by locally applicable regulations. Audits may be conducted at any time during or after the study to ensure the validity and integrity of the study data.

To enable evaluations and/or audits from regulatory authorities, the investigator agrees to keep records, including the identity of all participating patients, a record of sent patient information letters or all original signed informed consent forms, if applicable. After the database lock, however the connection between patient identity and collected data will be destroyed. Copies of all CRFs, source documents and adequate documentation of relevant correspondence (e.g., letters, meeting minutes, telephone calls reports) should be retained by the investigator according to local regulations, or as specified in the study contract, whichever is longer.

Each site will receive a study site file at study initiation which contains all documents necessary for the conduct of the study and this should be updated throughout the study. This file must be available for review in the event the site is selected for monitoring, audits, or inspections and must be safely archived for at least 10 years after completing the participation in the study or as per local regulations, whichever is longer. In the event that archiving of the file is no longer possible at the site, the site will be instructed to notify the Sponsor.

